### Measurements

1. Basic demographics: age, gender, marital status, education (years and highest attainment), and work experience.
2. Risk flowchart: a customized questionnaire for quick screening of the following known risk factors for late-life depression: recent spousal death; widowed; disability; living alone; pain & sleep complaints.
3. The Patient Health Questionnaire (PHQ-9) (Kroenke, Spitzer, & Williams, 2001): a 9-item instrument that incorporates depression diagnostic criteria with other leading major depressive symptoms, and rates the frequency of the symptoms which factors into the scoring severity index. PHQ-9 scores of 5-9, 10-14, 15-19, 20 and above represent mild, moderate, moderately severe, and severe depression.
4. Self-harm risk assessment: assessment by social service staff on participant’s risk of self-harm (yes or no answers to 10 items) and harm to others (yes or no answers to 4 items), and in the end social service staff will give an overall evaluation of suicidal risk score ranging from 0-No to 3-High.

5. Generalized Anxiety Disorder scale (GAD-7; Spitzer, Kroenke, Williams, & Lowe, 2006): a 7-item scale, responses to each item are rated on a 4-point Likert scale and range from 0 to 3. The following guidelines are recommended for the interpretation: 5-9 for mild anxiety, 10-14 for moderate anxiety, and 15-21 for severe anxiety.
6. Hong Kong Montreal Cognitive Assessment 5-Minute Protocol (HK-MoCA 5-Min) (Wong et al., 2015): a validated and reliable cognitive screen for stroke and transient ischemic attack, brief and highly feasible for telephone administration. It includes four items examining attention, verbal learning and memory, executive functions/language, and orientation extracted from the MoCA.
7. Name generator: asking participants to list out names of people who they would turn to when they feel down, and when they need help for trivial things.
8. UCLA loneliness scale (UCLA-3) (Hughes, Waite, Hawkley, & Cacioppo, 2004): a 3-item self-report measuring individual's perceived loneliness. Each item is evaluated with scores ranging from 0 (never) to 3 (often), total score is the sum of all items, and higher score indicates higher level of perceived loneliness.
9. EQ-5D-5L (Herdman et al., 2011): a measure of health-related quality of life at five dimensions (5D), each with five levels (5L) of problems, and the five dimensions are: mobility, self-care, usual activities, pain/discomfort, and anxiety/depression. The traditional Chinese version for Hong Kong developed by EuroQol Group would be used.
10. Lifeengagement: a semi-structured interview asking clients about their typical day activities in three domains, physical, social, and mental. A combination of being active in at least two domains would be used as one of the exit criteria.
11. Client Service Receipt Inventory (CSRI) (Chisholm et al., 2000): to collect the current types and level of services which comprise the care package of each participant, and a locally adapted short version would be developed for this purpose.

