#### Assessment Procedures

After basic screening, assessments will be conducted by trained social services staff and peer supporters employed by NGOs for the intervention group, and by trained research assistants employed by the University of Hong Kong for the control group.

For the intervention group, assessments will be conducted at baseline (T0/Intake), completion of intervention (4 weeks to 6 months, depending on individual condition) or drop-out (T1/Exit), and follow-up at 12 months (T2/FU). For control group, assessment would be conducted at T0 and T2.

Assessment for those with clinically significant depressive symptoms will last for about 90 minutes, and assessment for those at-risk of depression will last for around 60 minutes.

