#### Interventions

The intervention group will receive a collaborative stepped care programme provided by registered social workers and trained peer supporters from elderly or mental health service units (NGOs) according to level of risks, symptom severity, and intervention response. Home visits or other format of contact will be delivered by trained peer supporters employed by NGOs to detect and engage hidden cases.

For “at-risk” group, 4 weeks of “selective prevention” group sessions will be provided at the elderly service level by trained peer supporters with registered social worker supervision, on wellness topics tailored to the person’s concern as entry point, packaged with mental health information, followed by a review. If the review shows no significant improvement, a further 2-4 weeks of group plus individual casework sessions will be provided.

For people with depressive symptoms, we further divide them to “mild” and “moderate” groups. For mild group, 6-8 weeks of indicated prevention with psychoeducation or low-intensity psychotherapy would be provided. For moderate group, 6-8 weeks high- intensity cognitive behavioral therapy (CBT) would be provided. All intervention for depressed elderly would be conducted by registered social workers who are trained by this project and employed by the NGOs. The trained peer supporters will be matched to individual older adults to walk them through the process.

The control group will receive treatment as usual, which will be determined by the responsible worker from NGO units.

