### Data Analysis

We will generate descriptive statistics of the demographic and clinical variables at the baseline (T0/Intake) assessment. The independent sample t-test will be used to compare the means of continuous variables in the intervention and control groups; the chi-square test will be used to compare categorical variables; and Fisher exact test will be used for variables with low cell counts ( $n < 5$ ). For the majority of clinical scales that are ordinal in nature, the independent samples Mann-Whitney U-test will be used to examine whether the same distributions could

be assumed across groups. As observations at two /three time points are nested within individuals and individuals are nested within clusters (centers), changes in outcome measures, including PHQ-9 and GAD-7 scores, will be assessed by a three-level linear mixed model. Because the number of clusters is small, degree-of-freedom correction using the Satterthwaite method will be applied to the mixed models to maintain the desired type I error rate (Leyrat, Morgan, Leurent, & Kahan, 2017). We will use STATA 14.1 (StataCorp, 2015) for data analysis. For all the tests, the statistical significance level was set at .05.

To investigate engagement in the intervention versus control group, the following analyses will be conducted: (1) Cox proportional hazard regression analysis of the time to the primary endpoint of voluntary withdrawal from service; (2) Chi-square test of initial refusal of service by eligible participants after screening.

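### T0-to-T1 change in life engagement cannot be read as a programme effect, because the measure is also an exit criterion, T1 is the exit assessment, and controls have no T1

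*Combined protocol and SAP*

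**What the plan says.** Four parts of the combined protocol and SAP bear on this.

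- **Measurements, item 10.** Life engagement is "a semi-structured interview asking clients about their typical day activities in three domains, physical, social, and mental". The item continues: "A combination of being active in at least two domains would be used as one of the exit criteria". It gives no score and no cut-off for being active. The other exit criteria are not listed.
- **Assessment Procedures.** In the intervention arm the second assessment falls at "completion of intervention (4 weeks to 6 months, depending on individual condition) or drop-out (T1/Exit"), "and follow-up at 12 months (T2/FU"). In the other arm: "For control group, assessment would be conducted at T0 and T2".
- **Interventions.** The at-risk group has a 4-week course and then a review: "If the review shows no significant improvement, a further 2-4 weeks of group plus individual casework sessions will be provided". For mild symptoms: "For mild group, 6-8 weeks of indicated prevention with psychoeducation or low-intensity psychotherapy would be provided". The moderate group also has a 6-8 week course. No response-based extension is described for the mild or moderate group.
- **Data Analysis.** "changes in outcome measures, including PHQ-9 and GAD-7 scores, will be assessed by a three-level linear mixed model". The model takes two or three time points per person, so T1 data from the intervention arm enter it. Life engagement is neither named among the outcomes nor ruled out.

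**The concern.** An assessment triggered by reaching a threshold on a measure is not a fair reading of that measure. If a participant stays until rated active in two domains and T1 is then recorded, T1 picks out a favourable moment from that person's ordinary fluctuation. Intake has no comparable gate, so the T0-to-T1 difference can be positive with no programme effect.

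The usual protection would be a control assessment at the same time and under the same rule. Controls are assessed only at T0 and T2, so nothing offsets the selection.

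At stake is a claim under Objective 2, which covers wellbeing: a rise in life engagement from intake to exit could be reported as benefit when the exit rule may have supplied some or all of it.

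**Working it through.** The plan gives no expected value, rate or effect size for life engagement, so there is no figure of its own to reproduce. The check has two parts: does the rule bear on the timing of T1, and how large could the bias be if it does?

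**1. Does the rule bear on the timing of T1?**

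- *Pointing to yes.* The item calls this an exit criterion, and T1 is the exit assessment. Completion varies with individual condition. The at-risk course can be extended after a review. The described courses end by 4 + 4 = 8 weeks (at-risk) or 8 weeks (mild and moderate), yet completion may fall as late as 6 months, so something other than the standard course length sets exit for some people.
- *Pointing to no.* The courses are mostly of fixed length. The at-risk extension depends on lack of improvement, not explicitly on two active domains. T1 is also taken at drop-out, when the criterion need not be met.

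Some dependence of exit on response is therefore documented. How far this particular criterion drives it is not.

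**2. How large could the bias be?**

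Assumptions, none of them from the documents:

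- There is no true change.
- Each rating of active in two or more domains comes from a normal latent score with correlation ρ between occasions in the same person, ρ = 0.5 to 0.85.
- 50% are active on any one occasion.
- Exit, and T1, come at the first review that meets the rule, or at the last review regardless.

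*One fixed review.* T1 is a single unselected reading: 50% at T0 and 50% at T1. The bias is nil.

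*Two reviews, no drop-out.* A person is active at T1 if active at either review. With 50% prevalence, the chance of being inactive at both is 1/4 + arcsin(ρ)/(2π). Hence

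T1 proportion = 3/4 − arcsin(ρ)/(2π), and bias = 1/4 − arcsin(ρ)/(2π).

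| ρ | arcsin(ρ)/(2π) | T1 active | Bias |
|---|---|---|---|
| 0.5 | 0.083 | 66.7% | +16.7 points |
| 0.7 | 0.123 | 62.7% | +12.7 points |
| 0.85 | 0.162 | 58.8% | +8.8 points |

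Simulation of 200,000 people gave 67%, 63% and 59%, in agreement.

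*Two reviews, 20% drop-out.* If drop-outs stay at the baseline rate, the bias is multiplied by 0.8: 0.8 × 16.7 = 13.3 and 0.8 × 8.8 = 7.1 points. If drop-outs leave at a random one of the two reviews, half of them carry the full bias, so the multiplier is 1 − 0.2/2 = 0.9: 15.0 and 7.9 points.

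The range for two reviews and 0-20% drop-out is therefore about +7 to +17 points.

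*T2.* The 12-month reading is not triggered by the rule. With everyone followed, drop-outs included, it stays at 50% in every scenario.

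**The case against.** The strongest reply has four parts.

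- **The rule may not govern exit.** It is one of several criteria; the others, how they combine and how often they are checked are not given. The courses are largely time-based, and exit at a single fixed review gives no bias. This stands, and it is why the range must start at zero.
- **A real effect could also bring people to the threshold.** This stands. A reader might infer that the T0-to-T1 rise is produced by the rule and not by the programme. The documents do not support that. The rule can inflate the change, and T1 alone cannot separate the two sources.
- **Life engagement is not a named outcome.** Measurements also lists demographics and a risk screen, so being listed does not make an item an efficacy endpoint, and to call it a circular endpoint goes too far. This stands in part: the wording in Data Analysis leaves the outcome list open, and the analytic role of this measure is simply not stated.
- **Larger figures need a schedule the plan does not contain.** Six reviews, as with 4-weekly review to 6 months, would give 69-86% active at T1 from 50% at intake, a bias of +19 to +36 points. No section describes such a schedule, so these figures should not be attached to this trial.

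Two further inferences are tempting. One is that PHQ-9 and UCLA-3 are also caught at a favourable moment; this was not shown, and the plan does not say that either is an exit criterion. The other is that attending programme sessions counts as an active domain; the item asks about a typical day and does not say so.

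**Conclusion.** The concern holds in a limited form. Where the criterion affects when people exit, the T0-to-T1 change in life engagement can be biased upward with no programme effect, has no control counterpart, and cannot be read as evidence of effect.

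With 50% active at intake, the illustrative size runs from nil (one fixed review) to about +7 to +17 percentage points (two reviews, 0-20% drop-out). It rests on the assumed prevalence, within-person correlation and review schedule, and is not an estimate for this trial. The T0-to-T2 comparison between arms does not carry this bias. One measure is affected, at one time point, and its analytic role is unstated; nothing here touches the named outcomes PHQ-9 and GAD-7.

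**What to change.** Change the wording of Measurements item 10 and Data Analysis as follows:

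- State that life engagement at T1 serves the exit decision and is excluded from the efficacy models.
- State that, if life engagement is analysed as an outcome, only the T0-to-T2 change is used, in both arms.
- Label any reported T0-to-T1 change as descriptive and conditional on exit.

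The exit rule and the visits are left unchanged. A rule discounting programme sessions at T2 is not needed: the intervention ends by 6 months and T2 is at 12, and such a rule could treat the arms unequally.

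The cost is a few sentences of text. The sponsor gives up a T1 result for this measure that could not have been interpreted.

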### Data Analysis

We will generate descriptive statistics of the demographic and clinical variables at the baseline (T0/Intake) assessment. The independent sample t-test will be used to compare the means of continuous variables in the intervention and control groups; the chi-square test will be used to compare categorical variables; and Fisher exact test will be used for variables with low cell counts ( $n < 5$ ). For the majority of clinical scales that are ordinal in nature, the independent samples Mann-Whitney U-test will be used to examine whether the same distributions could

be assumed across groups. As observations at two /three time points are nested within individuals and individuals are nested within clusters (centers), changes in outcome measures, including PHQ-9 and GAD-7 scores, will be assessed by a three-level linear mixed model. Because the number of clusters is small, degree-of-freedom correction using the Satterthwaite method will be applied to the mixed models to maintain the desired type I error rate (Leyrat, Morgan, Leurent, & Kahan, 2017). We will use STATA 14.1 (StataCorp, 2015) for data analysis. For all the tests, the statistical significance level was set at .05.

To investigate engagement in the intervention versus control group, the following analyses will be conducted: (1) Cox proportional hazard regression analysis of the time to the primary endpoint of voluntary withdrawal from service; (2) Chi-square test of initial refusal of service by eligible participants after screening.

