## **Objectives**

1. To evaluate the effectiveness of a collaborative stepped care and peer support programme in engaging older people at-risk of or with depression.
2. To evaluate the efficacy of the programme in reducing symptoms/risks and promoting wellbeing in older people at-risk of or with depression.
3. To investigate the impact of the programme on care resources utilization in these older adults.

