### Participants

1. Intervention Group: older people at-risk of having depression (n=1,600) and those with clinically significant depressive symptoms (n=400) recruited from NGOs providing the intervention in four pilot districts in Hong Kong
2. Control Group: older people at-risk of having depression (n=400) and those with clinically significant depressive symptoms (n=100) referred by different NGOs in Hong Kong and recruited through open recruitment

The inclusion criteria are:

- age 60 years or above; and
- residing in Kwun Tong, Kwai Chung, Tseung Kwan O, or Sham Shui Po; and
- have one or more known risk factor(s) for developing depression; and/or
- have depressive symptoms of mild level or above; and
- able to give informed consent to participate

The exclusion criteria are:

- known history of autism, intellectual disability, schizophrenia-spectrum disorder,
- bipolar disorder, Parkinson's disease, or dementia
- (temporary exclusion criteria) imminent suicidal risk;
- and difficulty in communication

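### Does the intervention-only exit visit, or the lack of a risk-group term, leave the arm comparison in the mixed model open to distortion?

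*Combined protocol and SAP*

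**What the plan says.** The Assessment Procedures section gives the arms different schedules. The intervention group is seen at baseline (T0), at "completion of intervention (4 weeks to 6 months, depending on individual condition) or drop-out (T1/Exit"), and then at "follow-up at 12 months (T2/FU). For control group, assessment would be conducted at T0 and T2". Controls therefore have two visits and the intervention group three.

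The Data Analysis section carries this into the model: "As observations at two /three time points are nested within individuals and individuals are nested within clusters (centers), changes in outcome measures" are to be examined in a three-level linear mixed model with Satterthwaite degrees of freedom; PHQ-9 and GAD-7 are the outcomes it names. It names no fixed effects at all: not arm, visit, their interaction, or any covariate.

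The Participants section sets quotas by risk group. The intervention group is to include "older people at-risk of having depression (n=1,600) and those with clinically significant depressive symptoms (n=400"), and the control group "older people at-risk of having depression (n=400) and those with clinically significant depressive symptoms (n=100"). The Interventions section gives the at-risk, mild and moderate groups different programmes. The Objectives section states efficacy for both groups together: "To evaluate the efficacy of the programme in reducing symptoms/risks and promoting wellbeing in older people at-risk of or with depression".

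**The concern.** A visit that exists in one arm only can alter what an arm-by-time coefficient estimates. T1 also falls at a time that depends on the participant's course, including drop-out. If time is a straight line in months, an early drop in PHQ-9 at exit tilts the intervention slope and leaves the control slope alone. If all post-baseline visits are merged into one follow-up period, the exit value is averaged into the intervention arm's follow-up mean and has no counterpart in controls. The two codings can move the estimate in opposite directions, and a plan that names neither seems to let the choice be made after the data are seen.

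Two further points add to the unease. The 12-month visit has no stated origin. If it ran from exit in one arm and from intake in the other, even a visit-by-visit contrast would compare different lengths of follow-up. And a single pooled effect is 80% at-risk participants, although the groups receive different programmes. In a non-randomised study, a missed quota in one arm could then shift the pooled contrast. The result at stake is the main efficacy comparison.

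**Working it through.** The plan gives no effect size, SD or power calculation, so there is no figure of its own to reproduce. The means below are assumed and serve only to show how each coding behaves.

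**1. Effect of the coding.** From Assessment Procedures: intervention visits at 0, t and 12 months, control visits at 0 and 12, with t from 4 weeks (0.92 month) to 6 months. Assumed: both arms change by -1 point at T2 (no 12-month effect), the intervention change at exit is x = -1, -2 or -3, data are complete, and each person has a random intercept.

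- *Linear months.* If everyone exits at the same t, the intervention slope is [(t - m)x + (12 - m)(-1)] / S, where m = (0 + t + 12)/3 and S is the sum of squared deviations of the three times from m. The control slope is -1/12. The apparent effect over 12 months is 12 × intervention slope + 1. At t = 0.92: m = 4.31 and S = 89.2. For x = -1 the slope is (3.39 - 7.69)/89.2 = -0.048, and the effect is -0.58 + 1 = +0.42. At t = 6: m = 6, so T1 has no leverage and the effect is 0 for any x.
- *Baseline/follow-up.* The effect is (x - 1)/2 - (-1) = (x + 1)/2.
- *Categorical visit, T2 contrast.* The effect is (-1) - (-1) = 0 for any x and t.

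| Coding | x = -1 | x = -2 | x = -3 |
|---|---|---|---|
| Linear, all exits at 4 weeks | +0.42 | +0.88 | +1.33 |
| Linear, exits even over 4 weeks to 6 months | +0.21 | +0.47 | +0.73 |
| Linear, all exits at 6 months | 0 | 0 | 0 |
| Baseline/follow-up | 0 | -0.5 | -1.0 |
| Categorical, T2 contrast | 0 | 0 | 0 |

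The even-spread row, computed numerically, is the same to two decimals at within-person correlations of 0.3, 0.5 and 0.7.

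**2. Which coding the plan points to.** The Data Analysis sentence counts two or three time points, which are visits, not a time scale in months. Controls have T0 and T2 only, so T0-to-T2 change is the only change that both arms supply. An arm-by-T1 term cannot be estimated, because controls have no T1. What remains is a model with arm, T1, T2 and arm-by-T2, for which the shift is 0.

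**3. Origin of the 12 months.** If the clock started at exit, intervention T2 would fall at 12 + 0.92 = 12.9 to 12 + 6 = 18 months after intake, against 12 in controls. With an assumed shared drift of -1 point per 12 months, that gives 0.92/12 = 0.08 to 6/12 = 0.50 point of apparent benefit. If exits follow the at-risk course in the Interventions section (4 weeks, plus a possible 2-4 more, so 4 to 8 weeks), the range is 0.08 to 1.84/12 = 0.15. Controls have no exit, so intake is the only origin the two arms share. On that origin the difference is 0.

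**4. Risk group.** Planned at-risk share: 1,600/2,000 = 80% and 400/500 = 80%. With equal shares, a pooled contrast is not confounded by risk group. A shift needs a quota miss. If symptomatic people improve by an assumed 3 points more than at-risk people and controls are 30% symptomatic instead of 20%, the contrast moves by 3 × (0.30 - 0.20) = 0.3 point towards harm; at 10% it moves by 0.3 towards benefit.

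**The case for a change.** The strongest case for a change is that the text does not exclude the less suitable codings, that the main efficacy result depends on this model, and that one sentence would settle it. The timing point can be pressed further. If exits fall between 4 and 8 weeks, the linear-month figures rise to about 0.38, 0.81 and 1.24 for exit changes of -1, -2 and -3. The design is also non-randomised, with different recruitment routes in the two arms, so a quota miss is possible, and one pooled figure shows neither group's effect.

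What stands is that the coding, the target visit and the time origin are not written down. What does not stand is the step from there to a fault. The large figures need an analyst to pass over the visit structure that the plan describes and fit a straight line through an exit time that varies by person. The baseline/follow-up figure is an error only if the target is the 12-month effect. If the intervention arm really is better at exit, that coding answers a different question, about average benefit over follow-up, and the Objectives section names no time point.

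On risk group, the section lists no covariates of any kind, so the lack of this one is not a decision to exclude it. The pooled estimate answers the pooled objective, and nothing in the plan prevents reporting the groups separately. Making a contrast standardised to 80:20 the main result would turn recruitment quotas into a target population that the documents never state.

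**Conclusion.** No change is needed. The Data Analysis section is brief, and the analyst must supply the fixed effects, but the design leaves one natural arm contrast: the difference in T0-to-T2 change, with visit as a category. On that reading the exit visit shifts the contrast by 0, given complete data and T2 timed from intake in both arms. The apparent effects under other codings (up to 1.33 points of harm or 1.0 of benefit) rest on assumed means and on codings that the plan does not call for. The origin question has a ready answer in the only starting point both arms share. The planned 80:20 split is equal across arms, so risk group matters to the pooled contrast only if the quotas are missed, by 0.3 point per 10 percentage points under an assumed 3-point difference in improvement. The plan leaves a detail unstated; it does not state a rule that is wrong.

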## **Methods**

### Design

This study adopts quasi-experimental design and compares older adults at-risk of or with depression receiving the stepped collaborative care (intervention group) versus those receiving standard care (control group).

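### The three-level model does not require a centre-by-time effect, so the Satterthwaite correction does not secure the 5% error rate for the between-arm difference in PHQ-9 and GAD-7 change

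*Combined protocol and SAP*

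**What the plan says.** Under Design, the study is not randomised: "This study adopts quasi-experimental design and compares older adults at-risk of or with depression", with the stepped-care programme in one group and standard care in the other. Under Participants, the intervention group is "recruited from NGOs providing the intervention in four pilot districts in Hong Kong", so intervention centres lie wholly in one arm. Controls are "referred by different NGOs in Hong Kong and recruited through open recruitment", so some of them may belong to no centre.

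Under Assessment Procedures, the intervention group is measured at T0, T1 and T2, and controls at T0 and T2 only.

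Under Data Analysis, visits are nested in persons, who in turn belong to centres: "individuals are nested within clusters (centers), changes in outcome measures, including PHQ-9 and GAD-7 scores, will be assessed by a three-level linear mixed model". Since clusters are few, "degree-of-freedom correction using the Satterthwaite method will be applied to the mixed models to maintain the desired type I error rate". The level is common to all analyses: "For all the tests, the statistical significance level was set at .05".

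The section does not list the fixed effects, name the contrast that tests efficacy, or say whether centre enters as an intercept only or also with a time coefficient. It gives no number of centres and no ICC.

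**The concern.** Objective 2 asks whether the programme reduces symptoms. With baseline among the repeated observations, that is a difference between arms in change, which is an arm-by-time term. An arm main effect would average in the baseline visit.

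Arm is a between-centre factor on the intervention side. The relevant error for the contrast therefore includes how much the mean change differs from centre to centre. A centre intercept takes the same value at every visit and describes differences in level, not in change. A model with intercepts alone tests arm-by-time against within-person residual error, as if the 2,500 people were independent.

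Some variation in change between centres is to be expected from the design. Each NGO employs the staff who deliver the intervention and who assess its own clients. Intervention length varies from 4 weeks to 6 months. Usual care for controls is decided by the worker in each unit. If this variation is left out of the standard error, intervals for PHQ-9 and GAD-7 are too narrow and ordinary differences between centres can be read as a programme effect. This is separate from the confounding that any non-randomised comparison carries.

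**Working it through.** The plan has no sample-size or power calculation, so there is no derived figure to reproduce; .05 is a setting. The question is whether the described model delivers it.

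**Inputs from Participants and Data Analysis.** Intervention N1 = 1,600 + 400 = 2,000. Control N0 = 400 + 100 = 500. Alpha = 0.05.

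**Assumptions, not in the documents.** Two-sided test; everyone measured at T0 and T2; no true effect; centres of equal size within arm; K1 and K0 centres per arm; ρ = share of the variance of change lying between centres (the ICC of change).

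**Step 1: does the centre intercept reach the contrast?** With person i in centre j, score = fixed part + a_j + b_ij + e_ijt. The change T2 − T0 is the fixed part + (e_ij2 − e_ij0); both a_j and b_ij cancel. A generalised least squares check agrees. The variance of the arm-by-time estimate was 0.500 for centre-intercept variances of 0, 1, 5 and 20 alike, with or without the intervention-only T1 visit, and this equals the plain change-score variance. Adding a centre-by-time variance of 0.1 or 0.5 with 4+4 centres raised it to 0.60 or 1.00, matching 0.5 + 2 × 0.1 × (1/4 + 1/4) and 0.5 + 2 × 0.5 × (1/4 + 1/4).

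**Step 2: what does Satterthwaite do?** With intercepts only and T0/T2 data, df is about 2,000 + 500 − 2 = 2,498 and the critical value is 1.961, against 1.960 with no correction.

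**Step 3: true error rate.** In units of the variance of change:

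- variance the test uses: V_m = 1/2000 + 1/500 = 0.0025
- true variance: V_t = ρ(1/K1 + 1/K0) + (1 − ρ) × 0.0025
- error = 2 × [1 − Φ(1.96 / √(V_t/V_m))]

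Example, 8+8 centres and ρ = 0.01: V_t = 0.01 × 0.25 + 0.99 × 0.0025 = 0.004975; V_t/V_m = 1.99; 1.96/1.411 = 1.389; error 16.5%.

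Example, 4+4 and ρ = 0.05: V_t = 0.05 × 0.5 + 0.95 × 0.0025 = 0.027375; V_t/V_m = 10.95; 1.96/3.309 = 0.592; error 55.4%.

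| Centres | ρ = 0 | 0.001 | 0.005 | 0.01 | 0.02 | 0.05 |
|---|---|---|---|---|---|---|
| 4+4 | 5.0% | 7.3% | 16.5% | 25.7% | 38.0% | 55.4% |
| 8+8 | 5.0% | 6.2% | 10.9% | 16.5% | 25.6% | 42.2% |
| 20+20 | 5.0% | 5.5% | 7.3% | 9.6% | 14.2% | 25.4% |
| 40+40 | 5.0% | 5.2% | 6.1% | 7.2% | 9.5% | 16.0% |
| 4 intervention, all controls without a centre | 5.0% | 6.2% | 10.9% | 16.6% | 25.7% | 42.3% |

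Simulation of 20,000 null trials per setting agrees: for 4+4 and ρ from 0.001 to 0.05 it gave 7.6, 16.8, 25.8, 38.1 and 55.8%. With 30% of participants lost, 4+4 and ρ = 0.01 gives 20.5% instead of 25.7%.

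For scale, if the SD of change were 5 PHQ-9 points (an assumption), ρ = 0.01 means centre mean changes with an SD of 5 × √0.01 = 0.5 points.

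**Step 4: carrying centre variation into the test.** A comparison of centre mean changes with Welch-Satterthwaite df gave simulated error of 3.9 to 4.9% (4+4) and 4.9 to 5.3% (8+8) over ρ from 0 to 0.05. With 4+4 centres and pooled variance, df falls to 6 and the critical value rises to 2.45.

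**The case against.** A reader might infer that the plan specifies a wrong model and that its false-positive rate will far exceed 5%. The documents do not support that.

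- **Model form.** The text never says intercepts only and does not exclude a centre-by-time effect. This stands: the defect is a structure left open, not a documented wrong model. But an analyst who fitted intercepts only would be following the plan, and would lose the error control it claims.
- **Contrast.** The plan never writes an arm-by-time term. If change scores were the outcome, a centre intercept would itself be between-centre variation in change and the problem would vanish. That reading fits the text poorly: the lowest level is observations at two or three time points, which matches the raw visits, and change scores would leave each control with one value and no within-person level.
- **Size.** No centre count or ICC of change is given. At ICC 0 the error is 5.0%, and at 0.001 it is barely raised. This stands, so every percentage above is conditional.
- **Reach.** The only endpoint called primary is voluntary withdrawal from service, analysed by Cox regression. This point does not touch it; it concerns Objective 2.
- **Controls and remedy.** Openly recruited controls may have no centre, so a centre-level test needs a rule for them. The simulations tested centre-mean comparisons with equal centre sizes within arm, not the mixed model with a centre-by-time effect. Both limits stand.

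**Conclusion.** The concern holds in a conditional form. As written, the plan neither includes nor requires between-centre variation in change. Under the ordinary random-intercept reading, the Satterthwaite correction is nearly inert for the efficacy contrast, so its stated purpose is not secured for PHQ-9 and GAD-7. This is more than missing detail, because a fit that complies with the plan can lose the error rate the plan says it protects.

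How far the error departs from 5% cannot be settled from the documents. Over the layouts tabulated, from 4+4 to 40+40 centres, it runs from 5.0% (ICC 0), through about 5 to 7% (ICC 0.001), to 55% (4+4 centres, ICC 0.05); 8+8 centres with ICC 0.01 gives 16.5%. The plan itself calls the number of clusters small, which points away from the most favourable layouts, but a claim that false positives will certainly be far above 5% goes beyond the evidence.

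**What to change.** In Data Analysis:

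1. Name the arm-by-T2 term as the efficacy contrast for PHQ-9 and GAD-7.
2. Add a random centre-by-time effect (a centre-level coefficient for the post-baseline visits) to the centre and person intercepts.
3. Apply Satterthwaite to the arm-by-T2 contrast, so that its df reflect the number of centres.
4. State the number of centres per arm and how openly recruited controls enter, for example as individuals with no centre effect.
5. Give a fallback if the centre-by-time variance cannot be estimated: a centre-level analysis of mean T0 to T2 change with Welch-Satterthwaite df, keeping controls without a centre as individual observations and fixing the weighting in advance.

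The cost is some wording and one model term, then wider intervals and fewer df, which lowers power if centres are few. Because the mixed-model version was not simulated here, its error rate should be checked by simulation at the actual centre numbers and sizes. If a centre-by-time effect was always intended, writing it down costs nothing.
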